### **Extension Phase**

[figure not shown]
At the end of the Blinded Active-treatment Phase (Week 52), subjects who have a Mayo endoscopy score  $\leq 1$  will have the opportunity to participate in the Extension Phase. Subjects participating in the Extension Phase will continue to receive the same treatment assigned during the Blinded Active-treatment Phase for an additional 52 weeks (ie, Weeks 52 to 104).

### **Post-treatment Observational Follow-up Phase**

All subjects are required to spend 4 weeks in the Post-treatment Observational Follow-up Phase following the last dose of IP.

The study schematic is presented in [Figure 1](#) below.

**Figure 1: Overall Study Design**

## 4.2. Study Endpoints

### 4.2.1. Primary Endpoint

The primary endpoint of this study is the proportion of subjects achieving a clinical remission in the TMS at Week 12, defined as a TMS of  $\leq 2$ , with no individual subscore  $> 1$ .

### 4.2.2. Secondary Efficacy Endpoints

- The proportion of subjects achieving clinical response at Week 12, defined as a decrease from baseline in the TMS of at least 3 points and at least 30%, along with a reduction in the rectal bleeding subscore (RBS) of at least 1 point or an absolute RBS of  $\leq 1$
- The proportion of subjects achieving endoscopic remission at Week 12, defined as a Mayo endoscopic subscore of 0
- The proportion of subjects achieving endoscopic response at Week 12, defined as a decrease from baseline of at least 1 point in the Mayo endoscopic subscore
- The proportion of subjects achieving a RBS  $\leq 1$  at Week 12
- The proportion of subjects achieving clinical remission in the modified Mayo Score (MMS) (range: 0 to 9, based on stool frequency (SFS), RBS and endoscopy) at Week 12, defined as a score of 2 points or lower, with no individual subscore exceeding 1 point
- The proportion of subjects achieving clinical response in the MMS at Week 12, defined as a decrease from baseline at least 2 points and at least 25%, along with a reduction in the RBS of at least 1 point or an absolute RBS of  $\leq 1$  point

- The proportion of subjects achieving clinical remission at Week 8, defined as a partial Mayo score (PMS) of  $\leq 2$ , with no individual subscore  $> 1$
- The proportion of subjects achieving clinical response at Week 8, defined as a decrease from baseline in the PMS of at least 2 points and at least 25%, along with a reduction in the RBS of at least 1 point or an absolute RBS of  $\leq 1$  point

**4.2.3. Secondary Safety Endpoints**

- Type, frequency, severity, and relationship of AEs to IP
- Number of subjects who discontinue IP due to any AE
- Frequency of clinically significant changes in physical examination, vital signs, and/or laboratory findings

[Redacted content]

### 4.3. Stratification, Randomization, and Blinding

Approximately 165 subjects (55 subjects per arm) will be randomized in a 1:1:1 ratio using an IVRS/IWRS to receive oral apremilast (30 mg BID or 40 mg BID), or identically appearing placebo BID for up to 12 weeks, followed by 40 weeks of blinded treatment with apremilast (30 mg BID or 40 mg BID). At the end of 52 weeks in the study, subjects who have a Mayo endoscopy score  $\leq 1$  will have the opportunity to participate in the Extension Phase and will continue to receive the same treatment assigned during the Blinded Active-treatment Phase for an additional 52 weeks.

Treatment assignment will be stratified via IVRS/IWRS based on concomitant use of oral corticosteroids and previous exposure to immunosuppressants (eg, 6-MP, AZA, or MTX). The number of subjects with previous exposure to immunosuppressants is targeted to comprise, no more than 50% of the subjects enrolled, and no less than 30%.

### 4.4. Sample Size Determination

A 2-group chi-square test with a 0.1 two-sided significance level will have approximately 80% power to detect a true 20% absolute difference (30% versus 10%) between a dose of apremilast and placebo, for the proportion of subjects achieving a clinical remission at Week 12 when the sample size in each group is 49. Assuming a dropout rate of 10% prior to Week 12, approximately 165 subjects (approximately 55 subjects per group) are planned to be randomized in this study.

## 5. GENERAL STATISTICAL CONSIDERATIONS

### 5.1. Reporting Conventions

The following reporting conventions apply generally to tables, listings, and figures:

- Treatment comparisons between each apremilast group and the placebo group will be made for the efficacy analyses.
- Stratified analyses will use the 2 randomization stratification factors (concomitant use of oral corticosteroids [yes/no] and previous exposure to immunosuppressants [yes/no]), unless otherwise specified.
- Stratified analyses and subgroup analyses with respect to the 2 randomization stratification factors will be based on each subject's actual strata according to the clinical database of prior/concomitant medications, rather than the strata as randomized in the IVRS/IWRS.
- P-values will be 2-sided and presented with 4 decimal places. P-values that are rounded to 0.0000 will be presented as "< 0.0001" and p-values that are rounded to 1 "> 0.9999".
- Confidence intervals (CIs) will be presented as 2-sided 95% CIs.
- Summary statistics will consist of the number and percentage of subjects in each category for discrete variables, and the sample size, mean, standard deviation (SD), median, minimum, 25th percentile (Q1), 75th percentile (Q3), and maximum for continuous variables.
- All mean, median, Q1, Q3, and CI values will be formatted to one more decimal place than the measured value. Standard deviation values will be formatted to two more decimal places than the measured value. Minimum and maximum will be formatted to the same number of decimal places as the measured value.
- All percentages will be rounded to one decimal place. The number and percentage of responses will be presented in the form XX (XX.X), where the percentage is in the parentheses.
- Change from baseline is calculated as the post-baseline value minus the baseline value.
- All laboratory data will be reported using standard international units.
- All analysis and summary tables will include the analysis population sample size (ie, number of subjects) in the column headings.
- Listings will include both the randomized treatment and actual treatment.

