10.6. Efficacy Analysis

The ITT population (Section 10.2) will be the primary population for efficacy analyses. A supportive analysis using the PP population will also be performed for the primary efficacy endpoint.

The comparisons for the primary efficacy endpoint will be based on two-sided statistical tests at a significance level of 0.1. A hierarchical approach will be used to adjust for multiplicity. For the primary endpoint, the first test in the hierarchy will be the apremilast 40 mg BID treatment group compared to placebo, followed by the apremilast 30 mg BID treatment group compared to placebo. If any of the active treatment groups (apremilast 30 mg or 40 mg BID) is discontinued prior to the end of the study, the treatment comparison will be conducted for the retained treatment group vs. placebo based on a two-sided statistical test at the 0.1 level. Additional endpoints subsequent to the primary endpoint comparisons may be added to the hierarchy and specified in the SAP.

Summary of all efficacy endpoints over time will be provided using frequency and percent for categorical endpoints and descriptive statistics for continuous endpoints.

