## 11. EFFICACY ANALYSIS

### 11.1. Multiplicity

Formal statistical tests, conducted at a 2-sided significance level of 0.1, are planned between APR 40 BID and placebo and between APR 30 BID and placebo for the primary efficacy endpoint. To control the family-wise Type 1 error rate at the 0.1 level, these 2 formal statistical tests will be carried out by using a fixed sequence testing procedure, with the comparison between APR 40 BID and placebo tested first. The comparison between APR 30 BID and placebo will be tested only if the comparison between APR 40 BID and placebo is statistically significant. If any of the 2 apremilast dose groups is discontinued prior to the end of the study, the treatment comparison will be conducted for the comparison between the retained apremilast dose and placebo at a 2-sided significance level of 0.1.

For formal statistical tests that are planned but not performed as a result of the aforementioned multiplicity adjustment strategy, as well as for any other comparisons that are not subjected to multiplicity adjustment, nominal 2-sided p-values (without adjustment for multiplicity) will be provided as a measure of the strength of association between the endpoint and the treatment effect rather than formal tests of hypotheses.

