## **11.3. Analysis of Primary Endpoint**

### **11.3.1. Primary Analysis of Primary Endpoint**

The primary objective of the study will be evaluated by testing the superiority of each of the 2 apremilast doses over placebo with respect to the proportion of subjects achieving a clinical remission in the TMS, defined as a TMS of  $\leq 2$ , with no individual subscore  $> 1$ , at Week 12 based on the ITT population and the Cochran-Mantel-Haenszel (CMH) test stratified by the randomization stratification factors. Within-group proportions, 2-sided 95% CIs (based on the

Wilson score method) for the within-group proportions, unstratified treatment differences in proportions, stratified treatment differences in proportions using the weighted average of the treatment differences across the strata with the CMH weights, stratified 2-sided 95% CIs (based on the stratified Newcombe method [Yan, 2010]) for the treatment differences in proportions, and the 2-sided p-values from the CMH tests, will be provided. Missing data will be handled by the NRI approach.

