### 11.3.2. Sensitivity Analyses of Primary Endpoint

The following sensitivity analyses will be performed for the primary endpoint: 1) using the PP population and the NRI method for missing data; 2) using DAO (Section 11.2.2.2); 3) using the ITT population and the LOCF method for missing data (Section 11.2.2.2). The statistical methods adopted for the primary analysis will also be used for these sensitivity analyses.

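### Does testing the primary endpoint at two-sided 0.10 mean the SAP must also plan a 90% interval for the difference?

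*SAP*

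**What the plan says.** The test level is the same throughout. The Protocol (10.6) says that primary comparisons "will be based on two-sided statistical tests at a significance level of 0.1". SAP 4.4 sizes the trial on that basis: "A 2-group chi-square test with a 0.1 two-sided significance level will have approximately 80% power". SAP 11.1 fixes the order, with 40 mg first and 30 mg tested only if 40 mg succeeds: "Formal statistical tests, conducted at a 2-sided significance level of 0.1, are planned between APR 40 BID and placebo".

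The interval level is also the same throughout, but different from the test level. SAP 5.1 states: "Confidence intervals (CIs) will be presented as 2-sided 95% CIs". SAP 11.3.1 applies this to the primary difference, listing "stratified 2-sided 95% CIs (based on the stratified Newcombe method" next to the CMH p-value. SAP 11.3.2 carries it into the sensitivity analyses: "The statistical methods adopted for the primary analysis will also be used for these sensitivity analyses".

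Outside the formal sequence, SAP 11.1 says that "nominal 2-sided p-values (without adjustment for multiplicity) will be provided". For those results no declared significance exists for an interval to disagree with. Parts of the SAP's efficacy chapter are blacked out, but the primary-analysis section is readable. The readable text plans no 90% interval.

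**The concern.** A two-sided test at 0.10 pairs naturally with a 90% interval, since the two then exclude zero in nearly the same datasets. A 95% interval is wider. If the primary p-value falls between 0.05 and 0.10, the sponsor declares superiority, and for 40 mg also opens the 30 mg test, while the one interval in the table runs through zero. A reader may see a contradiction in the headline result. A 90% interval added after such a result would look chosen to suit it. What is at stake is how clearly a borderline win reads, and the remedy would be cheap, so the point deserves a check.

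**Working it through.** **Inputs.** From SAP 4.4: two-sided alpha 0.10, remission 30% versus 10%, 49 per group, 10% dropout, 55 randomized per group. From SAP 5.4.1 and 11.3.1: ITT with nonresponder imputation, so all 55 stay in the denominator. Stratum sizes are not given, so the main calculation is unstratified.

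**Step 1: reproduce the plan's sample size.** With mean rate 0.20 and a pooled-variance chi-square test:

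n = [1.6449·√(2·0.20·0.80) + 0.8416·√(0.30·0.70 + 0.10·0.90)]² / 0.20²
= [0.9305 + 0.4610]² / 0.04 = 48.4, so 49 per group.

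49/0.9 = 54.4, so 55 per group and 165 in three arms. The stated figures are reproduced.

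**Step 2: wins with p between 0.05 and 0.10.** The normal approximation with 55 per arm gives:

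- power at 0.10: Φ[(0.20·√55 − 0.9305)/0.5477] = 0.84356
- power at 0.05: Φ[(0.20·√55 − 1.1087)/0.5477] = 0.75294
- share of wins in between: (0.84356 − 0.75294)/0.84356 = 10.7%

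Exact enumeration of both binomials gives 0.8511 and 0.7718, so (0.8511 − 0.7718)/0.8511 = 9.3%.

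**Step 3: wins whose 95% Newcombe interval includes zero.** Over the same enumeration, a win is a chi-square p below 0.10 in favour of apremilast.

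| Setting | Power at 0.10 | Wins with p 0.05–0.10 | Wins with 95% interval including 0 |
|---|---|---|---|
| 30% vs 10%, n=55 | 85.1% | 9.3% | 11.2% |
| 30% vs 10%, n=49 | 81.4% | 11.0% | 12.7% |
| 27% vs 9%, n=55 (assumes the 10% dropouts count as nonresponders in both arms) | 80.8% | 11.6% | 13.9% |
| 22% vs 10%, n=55 (assumed smaller effect) | 53.1% | 23.1% | 26.9% |

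At the design effect with 55 per arm, 0.0950 of all comparisons are such wins, and 0.0950/0.8511 = 11.2%. With 90% Newcombe intervals the share is below 0.03% in every row.

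**Step 4: separate the two causes.** In row one, every win with p between 0.05 and 0.10 has a 95% interval that includes zero; that is the 9.3%. The other 1.8 points are wins with p below 0.05. For example, 14/55 versus 6/55 gives p = 0.048 and a 95% interval from −0.02 to 28.6 points. This disagreement between the chi-square test and the Newcombe method would also occur in a trial tested at 0.05 with 95% intervals.

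**Step 5: see what a reader would face.** Take 15/55 (27.3%) versus 7/55 (12.7%), a difference of 14.5 points.

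- Test: pooled rate 22/110 = 0.20; SE = √(0.20·0.80·2/55) = 0.0763; z = 1.907; p = 0.057.
- 95% lower limit: the Wilson limits needed are 0.1728 (lower, active) and 0.2402 (upper, placebo), so 0.1455 − √[(0.2727 − 0.1728)² + (0.2402 − 0.1273)²] = −0.005. The interval is −0.5 to 29.0 points.
- The 90% interval is 1.9 to 26.7 points.

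These statements agree with each other: zero is excluded at 90% and not at 95%, as a p-value of 0.057 implies.

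**Step 6: ask what the interval decides.** SAP 11.1 ties significance and the opening of the 30 mg comparison to formal tests at 0.10. SAP 11.3.1 names the CMH test as the basis for superiority. SAP 5.1 reports p-values to four decimals. No section uses an interval limit as a criterion, so replacing 95% by 90% leaves type I error, power and every declaration as they were.

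**The case for a change.** The strongest case for a change is that an estimate and interval are reported so that readers can judge size and precision beside the decision, and the plan gives none at the level of the decision. Stratification does not remove the mismatch. Simulating the planned CMH test and stratified Newcombe interval at 30% versus 10% with 55 per arm gives 11–12% of wins with a 95% interval including zero, against 0.3–1.0% with 90% intervals, for assumed stratum sizes. Group rates alone would let a reader rebuild an unstratified 90% interval, but not the stratified one. Fixing the level before unblinding would cost a sentence and a column.

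The arithmetic stands, and so does the remark that a matched interval is tidier. The step from there to a needed change does not. Nothing in the documents requires the test and interval levels to match. A sentence saying that the CMH p-value governs would largely restate SAP 11.1 and 11.3.1. A single 95% level also has a use: SAP 11.4 analyses the secondary endpoints in the same way as the primary, so one level keeps the tables comparable. In a Phase 2 trial with a relaxed 0.10 threshold, it also shows the uncertainty more cautiously. A borderline win that looks borderline is not misreported.

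**Conclusion.** The mismatch in levels is real in the readable text, but no change follows. It affects presentation only. At the design effect with 55 per arm, 11.2% of wins would show a 95% interval that includes zero; 9.3 points come from the 0.10/95% pairing and 1.8 from the test and interval not being exact inverses. These shares are per comparison, conditional on a win, and rest on the SAP's 30% versus 10% and an unstratified exact calculation. The higher shares need a diluted or smaller effect that the SAP does not assume. The decision rule is stated, the 95% interval is valid, and analysts following the plan reach the same conclusions with either interval. A 90% interval beside the 95% one would be a harmless reporting choice, with no gain in the inference.

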### 5.2. Safety Analysis Periods

For the safety analysis, the following analysis periods for post-baseline data are defined. Safety data in these periods are considered treatment-emergent.

- Weeks 0-12 placebo-controlled phase: This period encompasses data through Week 12. It starts on the date of the first dose of IP in the study, and ends on the date before IP dispensing at Week 12 for subjects who receive at least 1 dose of IP after Week 12 (defined as the date of the last dose of IP in the study no earlier than the date of IP dispensing at Week 12), or 28 days after the last dose of IP in the study or on the date of the actual last follow-up in the study, whichever comes first, for subjects who discontinue at or prior to Week 12.

Of note, this period is exclusive of the date of the first dose of IP in the study and inclusive of the date of IP dispensing at Week 12 for the analyses of the lab, vital signs, weight, and ECG data.

The safety analysis tables for the placebo-controlled phase will be presented by the following 4 groups: placebo, APR 30 BID, APR 40 BID, and APR total.

- Weeks 0-52 apremilast-exposure period: This period encompasses all apremilast-exposure data through Week 52, irrespective of when the apremilast exposure starts (at Week 0 or 12) in the study. It starts on the date of the first dose of apremilast in the study, and ends on the date before IP dispensing at Week 52 for subjects who receive at least 1 dose of apremilast after Week 52 (defined as the date of the last dose of apremilast in the study no earlier than the date of IP dispensing at Week 52), or 28 days after the last dose of apremilast in the study or on the date of the actual last follow-up in the study, whichever comes first, for subjects who discontinue at or prior to Week 52.

Of note, this period is exclusive of the date of the first dose of apremilast in the study and inclusive of the date of IP dispensing at Week 52 for the analyses of the lab, vital signs, weight, and ECG data.

The safety analysis tables, with an exception for the summaries of labs, vital signs, and body weight by time point, for the apremilast-exposure period during Weeks 0-52 will be presented by the following 4 groups: APR 30 BID, APR 40 BID, APR 30 BID/APR 40 BID, and APR total, as follows:

- The APR 30 BID group includes the data during the APR 30 BID treatment for subjects who receive APR 30 BID only in the study, subjects who initially receive APR 30 BID and switch to APR 40 BID at Week 12, and subjects who initially receive placebo and switch to APR 30 BID at Week 12.
- The APR 40 BID group includes the data during the APR 40 BID treatment for subject who receive APR 40 BID only in the study and subjects who initially receive placebo and switch to APR 40 BID at Week 12.
- The APR 30 BID/APR 40 BID group includes the data during the APR 40 BID treatment for subjects who initially receive APR 30 BID and switch to APR 40 BID at Week 12.
- The APR total group combines all the data of all the groups.

For the summaries of labs, vital signs, and body weight by time point, the data during the APR 30 BID and APR 40 BID treatments after Week 12 for subjects who initially receive

placebo and switch to APR 30 BID and APR 40 BID, respectively, at Week 12 will be summarized in the placebo/APR 30 BID and placebo/APR 40 BID groups, respectively.

- Weeks 0-104 apremilast-exposure period: This period encompasses all apremilast-exposure data through Week 104, irrespective of when the apremilast exposure starts (at Week 0 or 12) in the study. It starts on the date of the first dose of apremilast in the study, and ends 28 days after the last dose of apremilast in the study or on the date of the actual last follow-up in the study, whichever comes first.

Of note, this period is exclusive of the date of the first dose of apremilast in the study for the analyses of the lab, vital signs, weight, and ECG data.

The treatment groups presented in the safety analysis tables for the apremilast-exposure period during Weeks 0-104 will be the same as those for the apremilast-exposure period during Weeks 0-52.

- Weeks 52-104 apremilast-exposure period: This period encompasses the apremilast-exposure data during Weeks 52-104 and is to be summarized for subjects who receive at least 1 dose of apremilast after Week 52 (defined as the date of the last dose of apremilast in the study no earlier than the date of IP dispensing at Week 52). It starts on the date of IP dispensing at Week 52, and ends 28 days after the last dose of apremilast in the study or on the date of the actual last follow-up in the study, whichever comes first.

Of note, this period is exclusive of the date of IP dispensing at Week 52 for the analyses of the lab, vital signs, weight, and ECG data.

The safety analysis tables for the apremilast-exposure period during Weeks 52-104 will be presented by the following 3 groups: APR 30 BID, APR 40 BID, and APR total.

In the analyses of the lab, vital signs, weight, and ECG data, the value at the end of an analysis period is determined as the last post-baseline value among scheduled, unscheduled, and ET visits (excluding the follow-up visit) in the analysis period, whereas the worst value of an analysis period is determined among all visits (including the follow-up visit) in the analysis period.

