#### **Blinded Active-treatment Phase**

Following 12 weeks of treatment, subjects will enter the Blinded Active-treatment Phase for 40 weeks. At the Week 12 visit, subjects will be evaluated for clinical improvement based on the

TMS. The endoscopy subscore assessed by the investigator will be used for the calculation of the Week 12 TMS.

Subjects who achieve at least a 20% decrease from baseline in the TMS at Week 12 will receive the following IP between the Week 12 Visit and the Week 52 Visit:

- Subjects who were randomized to apremilast (30 mg BID or 40 mg BID) at baseline will continue to receive the treatment assigned at baseline.
- Subjects who were randomized to placebo at baseline will be re-randomized to receive apremilast (30 mg BID or 40 mg BID) and will be dose-titrated in 10-mg/day increments over the first 8 days of treatment.

Subjects who do not achieve at least a 20% decrease from baseline in the TMS at Week 12 will receive the following IP until the Week 52 Visit:

- Subjects who were randomized to apremilast 30 mg BID at baseline will be re-assigned apremilast 40 mg BID, with no dose titration.
- Subjects who were randomized to apremilast 40 mg BID at baseline will continue to receive apremilast 40 mg BID.
- Subjects who were randomized to placebo at baseline will be re-randomized to receive apremilast (30 mg BID or 40 mg BID) and will be dose-titrated in 10-mg/day increments over the first 8 days of treatment.

In order to maintain the blind for the treatment assigned at baseline, all subjects will receive blister cards of identical appearance during the titration period beginning at Week 12. However, for subjects continuing on the dosage of apremilast assigned at baseline, and for subjects who are not undergoing dose titration (as noted above), the IP included in the “titration” portion of the blister card will include the total daily dose of apremilast (30 or 40 mg BID) and will not include the dose titration.

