### 12.1. Adverse Events

AEs will be coded according to the MedDRA. Unless otherwise specified, AEs will be summarized by SOC and PT, with SOCs sorted in the standard international order and PTs within each SOC in descending order of subject incidence.

For the analyses of AEs, the following point estimates are provided, unless otherwise specified:

- Subject incidence: Subject incidence (i.e., percentage [%] used in a frequency summary) is defined as the number of subjects with the specific event divided by the number of subjects included in the analysis. Subjects with multiple occurrences of the specific event in the specific analysis period will be counted only once in the numerator.
- Exposure-adjusted incidence rate (EAIR) per 100 person-years: The EAIR per 100 person-years is defined as 100 times the number of subjects with the specific event divided by the total exposure time (in years) to the event among subjects included in the analysis. Subjects with multiple occurrences of the specific event in the specific analysis period will be counted only once in the numerator. The exposure time for a subject without the specific event is the duration of the specific analysis period as described in Section 5.2, whereas the exposure time for a subject with the specific event is the duration of the specific analysis period up to the start date (inclusive) of the first occurrence of the specific event. The total exposure time in years is calculated by dividing the sum of exposure time in days over all subjects included in the analysis by 365.25. The EAIR per 100 person-years is interpreted as the expected number of subjects with at least 1 occurrence of the specific event per 100 person-years of exposure to the event.

A subject data listing of all AEs (including treatment-emergent AEs [TEAEs] and non-TEAEs) will be provided.

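### The long-term AE columns for 30 mg and 40 mg differ in observation time and in response-based selection, so they are not a fair comparison of the two doses

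*SAP*

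**What the plan says.** SAP 4.1 (Blinded Active-treatment Phase) sets the Week 12 rule. It concerns "Subjects who do not achieve at least a 20% decrease from baseline in the TMS at Week 12". Among them, "Subjects who were randomized to apremilast 30 mg BID at baseline will be re-assigned apremilast 40 mg BID, with no dose titration"; those randomised to 40 mg stay on 40 mg. Placebo subjects are re-randomised to 30 mg or 40 mg with titration, whatever their Week 12 result.

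SAP 5.2 then builds the columns for the Weeks 0-52 safety tables:

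- **APR 30 BID.** "The APR 30 BID group includes the data during the APR 30 BID treatment". It covers 30 mg-only subjects, "subjects who initially receive APR 30 BID and switch to APR 40 BID at Week 12", and placebo subjects moved to 30 mg.
- **APR 40 BID.** "The APR 40 BID group includes the data during the APR 40 BID treatment for subject who receive APR 40 BID only in the study", plus placebo subjects moved to 40 mg. It is not split by Week 12 result.
- **Switchers.** "The APR 30 BID/APR 40 BID group includes the data during the APR 40 BID treatment" for those who changed dose.
- **APR total.** All of the above.

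The Weeks 0-104 tables use the same columns. For labs, vital signs and weight by time point, SAP 5.2 instead keeps the former placebo subjects apart: their data "will be summarized in the placebo/APR 30 BID and placebo/APR 40 BID groups, respectively".

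SAP 12.1 gives two estimates for each AE. Subject incidence is "the number of subjects with the specific event divided by the number of subjects included in the analysis". The exposure-adjusted incidence rate (EAIR) is events per 100 person-years, with time stopped at the first event.

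**The concern.** The rule that moves subjects out of the 30 mg column depends on outcome and has no counterpart on 40 mg. Two differences follow.

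- **Observation time.** Each 30 mg non-improver stays in the APR 30 BID head count with about 12 weeks of observation. The matching 40 mg subject is observed to Week 52.
- **Selection.** After Week 12, the subjects randomised to 30 mg at baseline who remain in that column are improvers only. The 40 mg column holds improvers and non-improvers.

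The switchers' column does not restore the balance, because 40 mg non-improvers have no parallel column. I found nothing in the SAP that warns of this. Long-term safety on the two doses is a secondary objective (SAP 3.2), and adjacent dose columns invite comparison. Two equally safe doses could look different, and the two planned estimates could point in opposite directions.

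**Working it through.** **Input from the plan.** The documents give no figure for these columns. The only stated number used is 55 per arm (SAP 4.4), which reproduces: [1.645 × √(2 × 0.2 × 0.8) + 0.842 × √(0.3 × 0.7 + 0.1 × 0.9)]² / 0.2² = 48.4, so 49 per group; 49 / 0.9 = 54.4, so 55; and 3 × 55 = 165.

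**Assumptions not in the documents.** Placebo subjects split equally (27.5 to each dose); no dropout; the same hazard on both doses and in improvers and non-improvers; non-improver share f = 20%, 35% or 50%. Each column then has 55 + 27.5 = 82.5 subjects.

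**Step 1, observation time.** Mean weeks per subject:

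- 30 mg: [55f × 12 + 55(1 − f) × 52 + 27.5 × 40] / 82.5 = 42.7, 38.7, 34.7
- 40 mg: [55 × 52 + 27.5 × 40] / 82.5 = 48.0

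**Step 2, incidence with a constant hazard.** At 40 per 100 person-years, λ = 0.40 × 7 / 365.25 = 0.00767 per week, and I(w) = 1 − exp(−λw) gives I(12) = 8.79%, I(40) = 26.41%, I(52) = 32.88%.

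- 40 mg: (55 × 0.3288 + 27.5 × 0.2641) / 82.5 = 30.7%
- 30 mg at f = 35%: (19.25 × 0.0879 + 35.75 × 0.3288 + 27.5 × 0.2641) / 82.5 = 25.1%

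The gap is (55f / 82.5) × [I(52) − I(12)] = 0.161f.

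| Non-improver share | 30 mg | 40 mg | Gap (points) | Ratio |
|---|---|---|---|---|
| 20% | 27.5% | 30.7% | 3.2 | 0.90 |
| 35% | 25.1% | 30.7% | 5.6 | 0.82 |
| 50% | 22.7% | 30.7% | 8.0 | 0.74 |

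**Step 3, EAIR for the same event.** With a constant hazard, expected on-dose time to first event or end of window is I(w)/λ. Events divided by time is therefore λ in both columns: 40 against 40 per 100 person-years, ratio 1.00 at every f.

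**Step 4, a front-loaded event.** Protocol 1.4.2 says that most diarrhea, nausea and headache began in the first 2 weeks. Take 15% in 2 weeks, then 10 per 100 person-years. Incidence is 16.6%, 21.0% and 22.8% at 12, 40 and 52 weeks; expected time at risk is 10.27, 33.00 and 42.37 weeks.

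| Non-improver share | Incidence 30 mg | Incidence 40 mg | EAIR 30 mg | EAIR 40 mg | EAIR ratio |
|---|---|---|---|---|---|
| 20% | 21.3% | 22.2% | 31.9 | 29.5 | 1.08 |
| 35% | 20.7% | 22.2% | 34.1 | 29.5 | 1.16 |
| 50% | 20.1% | 22.2% | 36.8 | 29.5 | 1.25 |

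Incidence is now only 0.8 to 2.1 points lower on 30 mg, while the rate is higher on 30 mg. The short windows of the switchers give the early weeks more weight in the 30 mg denominator.

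**Step 5, the exposure definition.** SAP 12.1 sets the exposure of an event-free subject to the length of the analysis period in SAP 5.2, and that period runs to Week 52. The column definitions point to on-dose time, but 12.1 does not say so. Read literally, an event-free switcher would bring 52 weeks instead of 12 to the 30 mg denominator, and the constant-hazard ratio of 1.00 would become 0.88, 0.79 or 0.71.

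**Step 6, dropout.** If half the 40 mg non-improvers left at Week 12 and nobody else did, the gap in Step 2 would halve to 1.6, 2.8 or 4.0 points.

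**The case against.** The strongest reply is that the plan already contains most of the protection needed. Safety is descriptive, with no testing (SAP 12). The long-term objective names subjects receiving either dose and states no comparison between doses. The Weeks 0-12 tables compare the randomised arms without this problem. EAIR is planned beside incidence, the switchers' later data are shown in their own column, and treatment duration is summarised (SAP 9.1). SAP 12.1.2 also tabulates all TEAEs for Weeks 0-104 by exposure interval, using as denominator the subjects who reach each interval.

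Much of this stands. The interval table deals with unequal windows and early weighting for all TEAEs. It does not remove the response-based selection after Week 12, and SAP 12.1.6 and 12.1.7 plan no such table for serious TEAEs or withdrawals. EAIR is a full correction only when the hazard is constant and equal in improvers and non-improvers.

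Three stronger readings are tempting, and the documents do not support them:

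- **That the tables will make 30 mg look safer.** This holds for incidence under the assumptions above, but the on-dose EAIR can be equal or reversed.
- **That events will drop out of the common-TEAE table.** SAP 12.1.3 lists an event that reaches the cutoff in at least one column, so a low 30 mg percentage does not remove an event that qualifies on 40 mg.
- **That non-improvers carry a much higher AE hazard.** The documents give no such figure, and Protocol 6.6.10 excludes UC worsening from AEs unless it is serious.

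**Conclusion.** The point holds as one about descriptive tables. The APR 30 BID and APR 40 BID columns differ by construction in observation time and in who remains after Week 12, and the SAP does not caution against comparing them. The Weeks 0-52 incidence gap is 3 to 8 points for a constant-hazard event and about 1 to 2 points for a front-loaded one. The EAIR ratio runs from 1.00 to 1.25 across these two cases if exposure is on-dose.

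The sizes rest on the assumed non-improver share, hazards, equal placebo split and absence of dropout. Only the structure comes directly from the SAP. The figures cover Weeks 0-52; I made no calculation for Weeks 0-104. A reader might infer that a planned long-term dose comparison is biased, but the plan states none, so the change is advisable and no formal conclusion of the trial depends on it.

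**What to change.** In SAP 5.2 and 12.1:

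1. Add the placebo/APR 30 BID and placebo/APR 40 BID groups to the TEAE, serious TEAE and withdrawal tables, measured from first apremilast dose through Week 52. Name this pair as the descriptive randomised dose comparison. The groups already exist for labs, vital signs and weight by time point.
2. Show the subjects randomised to apremilast at Week 0 by sequence: 30 mg only, 30 mg then 40 mg, 40 mg only.
3. State that EAIR exposure in each column is time on that dose.
4. Footnote the merged APR 30 BID and APR 40 BID columns as exposure summaries not meant for comparing doses.

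The cost is SAP wording and extra table columns; no new data are needed. The drawback is precision. With 55 × 0.9 / 2 ≈ 25 to 55 / 2 ≈ 28 subjects per re-randomised group, the 95% half-width for a difference near 30% incidence is 1.96 × √(2 × 0.3 × 0.7 / n), about 24 to 25 points, which is larger than the distortion being avoided. The pair also does not extend cleanly past Week 52, because extension entry depends on the endoscopy score and Amendment 4 puts all extension subjects on one dose.
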